### ***In-study risks and safety procedures:***

**General considerations:** Participant's treatment response as well as frequency and intensity of adverse effects will be discussed at baseline and assessed during follow-up visits with study staff. The study blind will be removed if any Unanticipated Problems Involving Risk To Subjects or Others (UPIRTSO) or adverse events is determined to be potentially related to the study medication (as deemed by treating study psychiatrist and study PI). Should concerns emerge regarding the patient's clinical problems not related to this study, those should be addressed by primary care specialist of patient's choice. If deemed necessary by study personnel, an urgent discussion with a study psychiatrist will take place for evaluation, and appropriate referral for treatment will be made. Study consent form includes participant's consent for permission to interface with his/her primary provider should clinical concerns arise.

**Depression Safety Management Plan:** The study team members will not be providing clinical care for conditions other than treatment of AUD and comorbid depression or anxiety. Therefore, any findings from PRISM assessment raising safety concerns, including positive response to suicide questions will trigger immediate notification to study psychiatrist and patient's clinician. In addition, if a subject endorses suicidality with any of the following: Active suicidal ideation as determined by the investigator or as determined by PHQ-9 (Question 9 score of 1 or higher) or if a subject responds positively to questions regarding the harm of self and/or others, the research team will immediately contact the study psychiatrist to refer for appropriate treatment.

During the follow up visits, questionnaires that involve questions related to depression not involving immediate concerns of harm to self or others will be reviewed within 1 working day of receipt from the subject. Changes reflecting worsening of depressive and anxiety symptom severity scores as collected using PHQ-9 and GAD-7, respectively, will be reported to the study psychiatrist who will determine if further assessment is necessary to ensure appropriate medical care and the safety of the study participant. The Clinical Global Impression (CGI) tool will be used to reflect assessment of those symptom changes by study psychiatrist. Study participants whose condition deteriorates to the point of being judged unstable (defined as a score of  $\geq 6$  on CGI) by a study psychiatrist, will be withdrawn from the study and referred to appropriate treatment. If emergent concerns arise regarding risk of harm to self or others, the patient will be referred for emergency care; if declined, authorities will be contacted for a well person check. Study PI or covering MD will be available to discuss questions related to management of depression, anxiety or other study-related aspects of patient care.

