**Table 1: Study Assessments**

Study Assessments	Baseline Evaluation	Follow-Up Visits					
		2 week – TC	1 month #	6 week – TC	2 month #	10 week – TC	3 month #
Blood Collection	X		X				X
Medication provided	X		X		X		
PRISM	X						
LTDH	X						
CIWA-Ar	X						
TLFB ♦ (BDQ)	X		X		X		X
PHQ-9	X	X	X	X	X	X	X
GAD7	X	X	X	X	X	X	X
AAM			X		X		X
IDTS	X						
PACS	X		X				X
PRISE	X		X		X		X
FIBSER			X		X		X
PSQI	X		X		X		X
FIRM	X						
CD-RISC	X						X
Med. Compliance			X		X		X
Med. Compliance Enhancement		X		X		X	
CTA	X						
GGT lab test	X		X				X
CTQ	X						
CGI			X**		X**		

**Definitions:** AAM: AA attendance monitoring. CIWA-R: Clinical Institute Withdrawal Assessment-Research. CTA: Commitment to Abstinence. CTQ: Childhood Trauma Questionnaire. FIBSER: Frequency, Intensity and Burden of Side Effects Ratings. GGT: gamma-glutamyl transpeptidase lab test. IDTS: Inventory of Drug Taking Situations. LTDH: Lifetime Drinking History. PACS: Penn Alcohol Craving Scale. PHQ-9: Patient Health Questionnaire 9-item. GAD7: Generalized Anxiety Disorder 7-item. PRISE: Patient-rated Inventory of Side Effects. PRISM: Psychiatric Research Interview for Substance and Mental Disorders. TC: Telephone Call TLFB: The Alcohol Timeline Follow Back. PSQI: Pittsburgh Sleep Quality Index. FIRM: Family Index of Risk for Mood. CD-RISC: Connor-Davidson Resilience Scale (CD-RISC); CGI: Clinical Global Impression (CGI); \*\*Used by study psychiatrist to assess worsening mood symptoms despite antidepressant treatment during study participation. ♦ Brief Drinking Questionnaire (BDQ). # Allow the use of alternative formats to face-to-face visits based on concern for COVID exposure or other circumstances potentially preventing patients from attending face-to-face visits (blood draw done in person).

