#### Analysis for Specific Aim 1b

Metabolite concentrations will be log-2 transformed, and associations between baseline metabolite concentrations and the time of abstinence since baseline will be evaluated by linear regression with age and gender as covariates. If Timeline Follow Back (TLFB) data at 3-months is absent, the date of last contact will serve as the day of first lapse unless the subject has reported a lapse at an earlier time point. To study the possible effect of depression severity and liver function, regression models including baseline PHQ-9 scores and LFTs (AST, ALT, and GGT) will be compared with those without to determine whether the metabolites remain significantly correlated with treatment outcome. Participants who provided paired blood samples will be classified as responders (maintenance of complete abstinence) or non-responders (any consumption of alcoholic beverages during the trial period), and their metabolite concentrations at baseline and at 3 months will be compared by two-way ANOVA to detect any significant changes between the two time points and whether these changes differ significantly between groups.

After metabolomic markers associated with length of sobriety (or additional secondary phenotypes) are identified, we will apply a “pharmacometabolomics-informed pharmacogenomics” research strategy. Specifically, we will perform genome-wide association analyses to search for genetic variants associated with metabolites that are associated with acamprosate clinical outcomes. We will then evaluate the association of the identified genetic variants ( $p < 5 \times 10^{-8}$ ) with clinical treatment outcomes in all available datasets (including the COMBINE and PREDICT datasets used in Aim 1a). We will also pursue all signals, genes and pathways functionally and mechanistically in order to investigate the biological mechanisms underlying sobriety length and other phenotypes associated with acamprosate treatment response. This is the same approach that we used previously with success to study biological mechanisms contributing to effects of selective serotonin reuptake inhibitors in patients with major depressive disorder (MDD).

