Table 2 Subject Characteristics	COMBINE	PREDICT	CITA
N	1393	426	443
Age, mean(SD)	44.4 (10.2)	45.3 (8.7)	42.1 (11.8)
Sex, N(%) male	955 (69%)	328 (77%)	286 (65%)
Race, N(%) white non-Hispanic	1062 (77%)	426 (100%)	412 (93%)
Baseline Consumption Measures (last 30 days)			
Average drinks per drinking day	13.0 (8.1)	19.4 (11.3)	11.8 (7.7)
% drinking days	72.8 (23.5)	82.1 (1.3)	50.7 (29.7)
% heavy drinking days	65.2 (24.9)	79.0 (1.3)	45.8 (29.7)
Number of days since last drink	7.7 (5.3)	22.1 (4.4)	24.8 (16.1)
Medications			
Acamprosate, N	608	172	443
Naltrexone, N	614	169	0
No active drug (placebo or no medication), N	466	85	0
Treatment outcomes			
3 month abstinence from any drinking, N(%)	293 (21.2)	194 (45.5)	132 (29.7)
3 month abstinence from heavy drinking, N(%)	432 (31.2)	210 (49.3)	168 (37.9)

For COMBINE and CITA, baseline consumption is based on 30 days prior to the start of medication, while for PREDICT it is based on 30 days prior to the onset of inpatient treatment, as proposed by Mann and colleagues (84).

For the COMBINE study, the number of participants for each medication may include participants on more than one medication (i.e. groups are not mutually exclusive since the study included acamprosate/naltrexone co-treatment).

Numbers for treatment outcomes are based on the ITT sample (i.e. complete sample) assuming those who dropped out prior to 3 months had returned to heavy drinking.

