#### Analysis for Specific Aim 2b:

Analysis for Aim 2b will use a similar strategy the analysis described above in aim 1b. However, in Aim 2b analyses will be performed on the much larger new sample and will also include assessment of drug interactions to evaluate whether metabolomics predictors of treatment outcome differ between acamprosate-treated and placebo-

treated patients. After identifying metabolites that predict treatment outcomes, we will again apply a pharmacometabolomics-informed pharmacogenomics analysis strategy, but genetic associations will be evaluated in the full sample of patients with genetic and treatment outcomes data, including the existing samples used in Aim 1 and the new samples collected in Aim 2.

Analysis for Specific Aim 3 will be completed in the future utilizing the latest methodology and analyses.

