### **Endpoints:**

The primary treatment outcome will be defined as continuous sobriety (yes/no) during 3 months of treatment.

Secondary outcomes (also assessed during 3 months of treatment) will include:

- (1) The number of days until first alcohol use assessed by TLFB.
- (2) Number of days until first relapse ( $\geq 5$  drinks/day for men and  $\geq 4$  drinks/day for women) will be assessed using TLFB.
- (3) Cumulative abstinence duration proportion: the proportion of days over the length of follow-up during which participants were completely abstinent from alcohol use, a score range of 0 (drinking continuously) to 100 (maintain complete abstinence) is applied.

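### Withdrawal for mood deterioration ends drinking follow-up, and the missing outcome is then coded as a lapse, excluded, or left uncoded, depending on the analysis

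*Combined protocol and SAP*

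**What the plan says.** **The rule.** The section on in-study risks and safety procedures covers "Study participants whose condition deteriorates to the point of being judged unstable", defined as a CGI score of 6 or more. Such participants "will be withdrawn from the study and referred to appropriate treatment". The wording is not limited to study medication, and no section provides for drinking data afterwards. Table 1 places the CGI at months 1 and 2, before the month-3 outcome, with the note "Used by study psychiatrist to assess worsening mood symptoms despite antidepressant treatment during study participation".

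**The endpoint.** "The primary treatment outcome will be defined as continuous sobriety (yes/no) during 3 months of treatment". The Endpoints section attaches no rule for missing data or withdrawal.

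**Handling of a missing month-3 outcome.**
- Aim 1b, length of abstinence: without a 3-month TLFB, "the date of last contact will serve as the day of first lapse", unless an earlier lapse was reported. The reason for the gap plays no part.
- Aim 2b: "Analysis for Aim 2b will use a similar strategy the analysis described above in aim 1b". The lapse rule is neither repeated nor withdrawn.
- Aim 2a, scan run first: acamprosate-treated participants with 3-month outcomes available.
- Aim 2a, secondary intention-to-treat analysis: everyone enrolled, with no stated code for dropouts. The rationale is that early dropout often follows relapse.
- Table 2, footnote 3: outcomes are counted "assuming those who dropped out prior to 3 months had returned to heavy drinking". This describes COMBINE, PREDICT and CITA.

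**The concern.** The removal is triggered by a psychiatrist's rating of mood, not by drinking. A participant who is sober when withdrawn has no month-3 TLFB, and the one explicit rule for that situation assigns a lapse date. The plan's reason for counting dropouts, that they have often relapsed, does not describe this person. Leaving such people out instead selects the analysed sample on mood.

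This trial is exposed to the problem because mood is part of its question. Aim 2a considers baseline PHQ-9 and GAD-7 scores as covariates and explores depression and anxiety as modifiers of genetic effects. The limitations section already concedes that the effects of depression and of its treatment cannot be separated. Adjustment for baseline scores does not remove worsening during the study. If withdrawal is related to genotype, metabolite level or arm, the consequence is bias. If it is related to none of them, the consequence is lost power.

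**Working it through.** **1. One sober participant withdrawn at month 2, followed through each analysis**

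| Analysis | What happens | Basis |
|---|---|---|
| Length of abstinence, Aim 1b approach used in Aim 2b | Lapse dated at last contact | Explicit in Aim 1b; reaches the new trial through Aim 2b's reference to a similar strategy |
| Responder comparison of paired samples (Aim 1b approach) | Not counted as a non-responder by withdrawal alone, since non-response means alcohol was consumed; no month-3 sample to pair | Explicit |
| Aim 2a scan run first | Left out | Explicit |
| Aim 2a Cox model for length of abstinence | Not stated | No censoring or event rule given |
| Aim 2a intention-to-treat | Not stated; relapse implied | The power argument treats dropout like non-response; the power statement splits an ITT sample into about 1/3 abstinent and 2/3 relapsed with no missing category; the only working definition of ITT is the Table 2 footnote on the earlier studies |
| Binary primary endpoint | Not stated | Endpoints section |

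**2. People affected under dropout-equals-relapse**

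Inputs: 800 participants (target accrual); one third abstinent (Aim 2a power statement). The withdrawal rate w is an assumption, 1% to 10%. Abstinence is assumed unrelated to withdrawal.

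Withdrawn = 800 × w. Abstainers miscoded = 800 × w / 3. Observed abstinence = (800/3 − 800w/3) / 800.

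| w | Withdrawn | Abstainers miscoded | Observed abstinence (true 33.3%) |
|---|---|---|---|
| 1% | 8 | 2.7 | 33.0% |
| 2% | 16 | 5.3 | 32.7% |
| 5% | 40 | 13.3 | 31.7% |
| 10% | 80 | 26.7 | 30.0% |

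**3. An unfavourable case for the link between depression and outcome**

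Assume also that one third of participants (267) have comorbid depression and that every withdrawal comes from them. True abstainers in that group: 267/3 = 88.9.
- w = 2%: (88.9 − 5.3)/267 = 31.3%. Odds ratio for sobriety against the true 1/3: (0.313/0.687)/0.5 = 0.91.
- w = 5%: (88.9 − 13.3)/267 = 28.3%. Odds ratio: (0.283/0.717)/0.5 = 0.79.

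These are depression-outcome odds ratios, not SNP-outcome odds ratios.

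**4. Power**

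The plan states 80% power for 1000 acamprosate-treated participants (ITT), one third abstinent, significance level 5 × 10⁻⁸, at odds ratio 2.07 (MAF 0.2) and 1.80 (MAF 0.4). An expected-data likelihood-ratio calculation (per-allele logistic model, Hardy-Weinberg genotypes, 1-df two-sided test) gives 78.2% and 71.4%. The first is close to the stated 80%; the second is not reproduced. That gap is separate from this point, so the computed values serve as the reference.

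Withdrawal is taken as unrelated to genotype and true drinking. Scored as relapse, abstinence for each genotype is multiplied by (1 − w). Left out, N becomes 1000(1 − w).

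| w | MAF 0.2: scored as relapse | MAF 0.2: left out | MAF 0.4: scored as relapse | MAF 0.4: left out |
|---|---|---|---|---|
| 0 | 78.2% | 78.2% | 71.4% | 71.4% |
| 1% | 76.7% | 77.2% | 69.9% | 70.4% |
| 2% | 75.1% | 76.3% | 68.2% | 69.3% |
| 5% | 70.2% | 73.2% | 63.2% | 66.1% |
| 10% | 61.4% | 67.6% | 54.4% | 60.2% |

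The rate is applied to all 1000, although the CGI rule governs only the new trial's participants, so these losses overstate the effect on the meta-analysis.

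**5. Could a depression variant look like a response variant?**

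Take the unfavourable case of step 3, MAF 0.3 and a per-allele odds ratio for depression of 1.2, 1.5 or 2.0 (assumptions). Withdrawal among depressed participants is 3w. Observed abstinence for genotype g is (1/3) × [1 − 3w × P(depressed given g)]. The induced per-allele odds ratio for abstinence is:
- w = 2%: 0.996, 0.992, 0.986
- w = 5%: 0.991, 0.979, 0.965

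The plan's own detectable odds ratios are 1.80 to 2.07.

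**The case against.** A reader might infer that the plan as a whole scores psychiatric worsening as alcohol relapse. The documents do not support that. The Aim 2a scan run first omits these participants, the responder comparison requires actual drinking, the Aim 2a Cox models can accommodate censoring, and the Table 2 footnote is about earlier studies. Only the length-of-abstinence rule codes a lapse explicitly. It is written for the CITA data and reaches the new trial by reference.

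A reader might also infer that depression variants would surface as acamprosate-response variants. Step 5 does not bear this out: the induced odds ratios are very near 1. If coding is the same in both arms, it would not by itself imitate a drug-specific effect unless withdrawal differs by arm.

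The step 3 figures need 6% to 15% of depressed participants to reach the threshold. The exclusion of unstable psychiatric conditions, the offer of antidepressant treatment and the frequent PHQ-9 and GAD-7 checks may make that high. If deterioration and drinking go together, fewer than one third of those withdrawn would be true abstainers, and a lapse already reported keeps its own date. Consent pages are not in the reviewed text, so terms for contact after withdrawal may exist there.

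All of this limits the scope and size of the point. It does not supply a drinking outcome for a sober person withdrawn for mood, and it does not remove the lapse date assigned to that person.

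**Conclusion.** The point holds in limited form. Withdrawal for mood deterioration is an intercurrent event that the plan does not handle consistently: a lapse in the length-of-abstinence analysis, an exclusion in the Aim 2a scan run first, and no stated code (relapse by implication) for the intention-to-treat analysis and the binary primary endpoint. In the first case a stated rule gives a sober participant a wrong value, so this is more than a missing detail.

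The size rests on an assumed withdrawal rate. Under relapse coding at MAF 0.2, power falls by 1.5 to 3.1 percentage points at 1-2% (78.2% to 76.7% or 75.1%) and by 8.0 to 16.8 points at 5-10% (to 70.2% or 61.4%), with the rate applied to the whole pooled sample. Bias beyond lost power requires withdrawal to be related to genotype, metabolite or arm, which the documents neither establish nor rule out. False genome-wide associations are not shown. The change is worth making because it is cheap and the phenotype is what every aim depends on. Nothing here bears on the clinical threshold.

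**What to change.** Leave the CGI threshold, the treatment decision and the referral as they are. Then:

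1. Separate leaving study treatment from leaving outcome follow-up. Ask participants who consent to give TLFB data, or the BDQ if they refuse the TLFB, at the remaining scheduled visits or at least once at month 3. Table 1 already says "Allow the use of alternative formats to face-to-face visits". The TLFB is described as retrospective for up to 12 months, so one month-3 contact could cover the whole period.
2. Use observed drinking for all endpoints, whether or not the participant is still on study treatment.
3. Record mood deterioration as its own withdrawal reason and report it by arm.
4. Where no later data are obtained, do not apply the last-contact lapse rule to these withdrawals. Censor at last contact in the Cox models. Treat the binary endpoint and the abstinence time used in linear regression as missing, since censoring cannot be applied directly to either.
5. Add a sensitivity analysis under dropout-equals-relapse, and write the code for dropouts into the intention-to-treat definition.

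Cost: protocol and analysis wording, and at most the three TLFB contacts already scheduled (months 1, 2 and 3), for what are probably few people. Some will decline, some drinking data will be off treatment, and censoring at psychiatric deterioration may be informative, which is why the sensitivity analysis is needed.

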### **Resources:**

We will utilize substantial resources available at Mayo Clinic, such as the Clinical Research Unit (CRU), to support recruitment and proper specimen collection and procurement at the Mayo Health System sites. The addition of the large clinical operation at the Hazelden Betty Ford Foundation treatment facilities in Center City and Plymouth, MN will significantly increase the referral base allowing for a more rapid achievement of the recruitment targets; and trained personnel (in all research sites) enabling large-scale prescreening, selection, enrollment and monitoring of the study participants will be required to achieve this goal. Adding Hazelden St. Paul location will improve visit options for patient travel while participating in the study.

Genome-wide genotyping will be conducted by the Mayo Clinic 'Medical Genome Facility', which offers a variety of genotyping assays, including state-of-the-art genome-wide SNP arrays.

The amino acid metabolomic platform assays using the CITA samples will be performed at the Mayo Clinic Metabolomic Core Facility. During year 2, metabolomic assays for neuromodulator metabolites will be performed. The acamprosate placebo-controlled trial recruitment will continue throughout years 1, 2 and 3—with completion of the trial at the end of year 3.

The Statistics Team, which will be responsible for data management, biostatistics and bioinformatics support. The statistical team ([name], Postdoc, MS Statistician, and Statistical Programmer) will meet weekly to plan and review ongoing data analyses. [name], the Statistics Team Director and Co-PI for this study, obtained a PhD degree in biostatistics, with a focus on statistical genetics, followed by further training in statistical genetics as a postdoctoral research fellow. She joined Mayo Clinic's Program in Genomics of Addiction ten years ago.

(1a) This is a multisite study involving Mayo Clinic and non Mayo Clinic sites. *When checked, describe in detail the research procedures or activities that will be conducted by Mayo Clinic study staff.*

(1b) Mayo Clinic study staff will be engaged in research activity at a non Mayo Clinic site. *When checked, provide a detailed description of the activity that will be conducted by Mayo Clinic study staff.*

### Subject Information

Target accrual: 800 (400 Mayo Clinic; 400 Hazelden Addiction Treatment Centers)

Subject population: Adults (male and female)

#### Inclusion Criteria:

1. Age 18 to 85; DSM-5 (14) diagnosis of AUD determined by PRISM;
2. Completion of alcohol detoxification (CIWA score < 5) and no alcohol for at least 7 days (but no more than 35 days);
3. Ability to provide informed consent
4. Ability to speak English
5. Willingness to use the study medications for 3 months and attend follow-up visits.
6. No chronic/daily use of benzodiazepines, opioids, or stimulants for a period of time which is determined by 3 x the medication half-life value (see addendum A) to be completed before the initiation of study medication (acamprosate or placebo).
7. Willingness to discontinue previously prescribed acamprosate for a period of at least 3 days before randomization to study medication (acamprosate or placebo\*) which allows for metabolomic signature without medication.

\*Notation dated 5-12-2023: Upon IRB approval, subjects will no longer be randomized to the placebo arm. Instead, for the remainder of the study, all patients will be provided acamprosate to achieve the active drug and placebo ratio of 2:1.

